6. SUBJECT RECRUITMENT & SCREENING

Based on a power analysis, 64 participants are needed with an expected attrition rate of 20% increasing the total number of participants to 78, with 26 in each of three groups.

Participants will be fluent in English, males and females age 18 years and older. The study will include participants from any race or ethnicity that meet eligibility criteria and demonstrate a positive Phalen's Test or positive Tinel's Test. The study population includes individuals who have symptoms of or have received a diagnosis of carpal tunnel syndrome, or experience forearm wrist hand pain and currently not receiving treatment. If participant has symptoms in both extremities, the researcher will use each extremity as a separate unit and apply corresponding intervention to both extremities.

Participants will be recruited using snowballing and judgmental sampling via word-of-mouth, flyers, emails, and social media with a \$5.00 gift card provided per visit for each of the five visits for the study. Flyers will be distributed throughout the Southern California area due to proximity but participants may come from any region if satisfying inclusion criteria and time commitment. Flyers will be placed in, but not limited to, common public places such as pet grooming places, community postings, manufacturing facilities, clinics, hair stylists, dental hygienists, sonographers, office buildings, and more. The principal investigator or appropriate personnel for Loma Linda University, and by the student researcher or appropriate personnel for the Stanbridge University access will acquire email addresses of potential participants. Specific social media outlets will include posting on but not limited to, Facebook, Instagram, and Twitter, with a website that will be accessed at: carpaltunnelstudy.wordpress.com for information. The contact information of the principal

investigator and student researcher will be available on the flyer with an invitation to contact researchers with any questions about the study.

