9. Week One Visit Two a student researcher and/or student research assistants will remove Kinesio Tape, check splints, and collect symptom journals and the Usual protocol group Splint-wearing and Exercise journal. Participants will complete Boston Carpal Tunnel Questionnaire, Numeric Pain Rating Scale, Visual Analogue Scale. Grip and Pinch measurements will be recorded.

Student researcher and/or student research assistants will re-apply Kinesio Tape and check splint and exercises resumed with the Usual protocol group.

Total exposure to application and removal of Kinesio Tape is four times as participants return every third day of Weeks One and Two.

10. Week Two Visit Three a student researcher and/or student research assistants will remove Kinesio Tape, check splints, and collect symptom journals and the Usual protocol group Splint-wearing and Exercise journal. Participants will complete Boston Carpal Tunnel Questionnaire, Numeric Pain Rating Scale, Visual Analogue Scale. Grip and Pinch measurements will be recorded.

Student researcher and/or student research assistants will re-apply Kinesio Tape and check splint and exercises resumed with the Usual protocol group.

11. Week Two Visit Four a student researcher and/or student research assistants will remove Kinesio Tape, check splints, and collect symptom journals and the Usual

protocol group Splint-wearing and Exercise journal. Participants will complete Boston Carpal Tunnel Questionnaire, Numeric Pain Rating Scale, Visual Analogue Scale. Grip and Pinch measurements will be recorded.

Student researcher and/or student research assistants will re-apply Kinesio Tape and check splint and exercises resumed with the Accepted protocol group.

12. Week Three Visit Five a student researcher and/or student research assistants will remove Kinesio Tape, check splints, and collect symptom journals and the Usual protocol group Splint-wearing and Exercise journal. Participants will complete Boston Carpal Tunnel Questionnaire, Numeric Pain Rating Scale, Visual Analogue Scale. Grip and Pinch measurements will be recorded.
13. Up to 26 participants from the Intervention group will be invited to participate in a 30-minute semi-structured audio-recorded interview with student researcher (Appendix N).
14. Email Reminder Script regarding study date (Appendix O)
15. See Timeline (Appendix P)

- d. Concise review of literature that supports the rationale, objectives, and methodology of the proposed study.

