11. DATA ANALYSIS

The research analysis plan will include a repeated measures multi-factorial analysis of variance to analyze continuous data for the functional grip and pinch measurements, with an analysis of covariance to rule out any confounding variables between groups. For Objective 1 of the randomized controlled trial of the study continuous data will be analyzed with change score analysis from baseline to end of study. To compare groups post-hoc Bonferroni will be used. Non-parametric statistics using the Friedman's Test will be used with the Numeric Pain Rating Scale, Visual Analogue Scale, and Boston Carpal Tunnel Questionnaire.

For Objective 2, qualitative data will be analyzed for thematic coding. Transcripts will be individually read and coded for emerging themes by the research team and then analyzed as a group to increase rigor. For Objective 3 to explore concepts of adherence to interventions with carpal tunnel syndrome, triangulation will be used with data obtained through interviews and with journals using a deductive approach to explore Kinesio Tape on performance. Data will be analyzed until redundancy is achieved.

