12. RISK AND INJURY

Participants may experience discomfort or skin irritation from wearing the tape, splint or completing the exercises. Participants may also experience fear and/or anxiety, and/or hyperventilation before during, or after application of Kinesio Tape, and/or splint, and/or exercises. Under these circumstances the Kinesio Tape will be removed from the participant's forearm wrist hand and provide first aid and seek medical care as needed. To minimize the potential of risks to participants the student researcher and student research assistants will ask if any known allergies to adhesives. Participants with a history or current allergy to adhesives will be excluded from the study. Risks may also include a participant may feel uncomfortable answering questions during interviewing. Loss of confidentiality may occur if two participants know each other. In order to protect confidentiality a number will be assigned to each participant. The master list and Informed Consent will be kept separate in the Principal Investigator's office.

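### Friedman's Test for the pain and function scales omits participants with a missed visit and gives no comparison of the three arms

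*Combined protocol and SAP*

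**What the plan says.** Section 11 (Data Analysis) assigns three outcomes to one method: "Non-parametric statistics using the Friedman's Test will be used with the Numeric Pain Rating Scale, Visual Analogue Scale, and Boston Carpal Tunnel Questionnaire". The same section reserves repeated measures analysis of variance and analysis of covariance for grip and pinch. It applies a change score from baseline to the end of the study to continuous data, and mentions Bonferroni post-hoc comparisons of groups.

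The three scales are taken at baseline. Section 8c, steps 9 to 12, then repeats for Visits Two to Five: "Participants will complete Boston Carpal Tunnel Questionnaire, Numeric Pain Rating Scale, Visual Analogue Scale". Section 9 describes the timing of the pain scales differently, as baseline and weeks one, two and three. It calls the data from these scales ordinal and describes the Boston questionnaire as using an ordinal scale.

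Section 6 gives the sample size: "Based on a power analysis, 64 participants are needed with an expected attrition rate of 20" per cent, "increasing the total number of participants to 78, with 26 in each of three groups". It also makes each hand a separate unit when both are symptomatic, with the same intervention on both.

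Section 12 covers discomfort, skin irritation, anxiety and hyperventilation: "Under these circumstances the Kinesio Tape will be removed from the participant's forearm wrist hand". It does not say what happens to outcome collection afterwards.

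The document gives no analysis set, no rule for missing scores, no statement that participants are analysed as randomised, and no alternative test for incomplete series.

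**The concern.** Objective 1 asks whether dorsal taping changes pain, strength and function. Pain (two scales) and function (the Boston questionnaire) both go through Friedman's Test, which has two properties that do not suit the task.

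First, it ranks scores within complete rows. A participant without a score at one of the visits entered is left out, including every score already given. The plan itself expects a fifth of participants to be lost and uses that figure only to raise enrolment. Larger enrolment restores numbers. It does not restore the randomised comparison if those who leave differ from those who stay.

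Second, it asks whether scores differ between visits. Treatment group does not enter it. A fall in pain over three weeks would be detected in any arm, or in the arms pooled, but the test cannot say whether the fall was larger with dorsal tape than with sham tape or with splint and exercises.

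**Working it through.** **Inputs.** 64 needed, 20% attrition, 78 enrolled as 3 x 26 (section 6); five scoring occasions (section 8c); Friedman's Test (section 11).

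**1. The plan's own figure.** 64 x 1.20 = 76.8, rounded up to 77, then to the next multiple of three: 78. The stated total is reproduced. Dividing instead gives 64 / 0.80 = 80, or 81 for three equal groups. The 64 itself cannot be rebuilt, because the document gives no effect size, SD, alpha, power or endpoint for it.

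**2. What the test uses.** With n complete rows, k visits and R_j the sum of within-row ranks at visit j, the statistic (without ties) is 12 / [n k (k + 1)] x sum of R_j squared, minus 3 n (k + 1). Two things follow. n counts only rows with all k scores, and no term refers to treatment group.

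**3. Check in software.** One simulated arm of 26 with five visits, 5 participants lacking the last visit:
- incomplete rows left in: statistic undefined;
- incomplete rows omitted: chi-square 7.473, p = 0.113, identical to the result on the 21 complete rows;
- all 26 complete, for comparison: chi-square 5.964, p = 0.202.

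The data were random, so the p-values have no meaning beyond showing that 21 rows, not 26, were used.

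**4. Size at the plan's attrition.**
- Complete: 78 x 0.80 = 62.4 (26 x 0.80 = 20.8 per arm).
- Omitted: 78 - 62.4 = 15.6, about 16 (15.6 / 3 = 5.2 per arm).
- Against the stated need: 64 - 62.4 = 1.6 short. The 14 added places cover 14 / 78 = 17.9% loss.

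**5. If participants who reach Visit Five also miss intermediate visits.** The document gives no rate for this. Assume independent misses at Visits Two, Three and Four:
- 2% per visit: 62.4 x 0.98^3 = 58.7
- 5% per visit: 62.4 x 0.95^3 = 53.5
- 10% per visit: 62.4 x 0.90^3 = 45.5

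The plan does not say which visits enter the test. If only the four time points in section 9 enter, two are intermediate, and the 5% and 10% figures become 62.4 x 0.95^2 = 56.3 and 62.4 x 0.90^2 = 50.5.

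**6. Unit.** These are counts of participants. If each hand is a row, a bilateral participant who leaves removes two rows, and rows from the same person are treated as independent.

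**The case against.** The strongest reply is that no sentence says leavers will be excluded. That is correct. The exclusion follows from the named test together with the absence of any other rule. An imputation or a Skillings-Mack test would avoid the omission, but neither is planned, and choosing one after seeing the data is what a plan should prevent. Neither would supply a comparison of arms.

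It can also be said that section 11 contains a change score and Bonferroni group comparisons, which may have been meant for these scales too. As written, the change score is for continuous data, while section 9 treats these scales as ordinal. Bonferroni is a multiplicity adjustment and does not name a test. A change score would also need the final visit.

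Enrolment was raised for attrition, so the loss of precision at 20% is small (62.4 against 64). This stands. The main harm lies in selection and in the missing arm comparison.

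Some stronger readings are tempting but unsupported:
- A reader might infer from section 12 that removing the tape ends participation. It says only that tape is removed and care given, and section 8c sets no condition of continued wear for completing the scales.
- A reader might infer that irritation falls on the tape arm alone, so that bias favours tape. Section 12 lists discomfort and irritation for tape, splint and exercises, and the sham arm also wears adhesive. The direction is unknown.
- A reader might infer that the planned test will hide or create a difference between arms. It produces no such difference; that risk belongs to any completers-only comparison put in its place.
- A reader might infer that emailed questionnaires would recover most of the lost scores. Nothing in the document supports a recovery rate.

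**Conclusion.** The point holds in this form. As planned, the pain and function results would rest on participants with complete series: about 62 of 78 at the plan's own attrition, with about 16 omitted although they have a baseline and possibly later scores. Under assumed miss rates of 5% or 10% at three intermediate visits, the number falls to about 53.5 or 45.5. These two figures are illustrations; the 62.4 depends on the stated 20% and on the last visit being among those entered.

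The size of any bias cannot be calculated from the document. It arises if leaving is related to arm or to lack of relief, and its direction is not known.

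The second half of the point needs no assumption about missing data. With every score present, Friedman's Test would still give no between-arm result for two of the three parts of Objective 1. This is the larger of the two defects, and one change of method repairs both. It should be made before analysis.

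**What to change.** **Section 11.** Replace Friedman's Test for the Numeric Pain Rating Scale, Visual Analogue Scale and Boston questionnaire with a linear or ordinal mixed model that uses every observed visit. Include group, visit, group-by-visit and baseline terms, and a participant effect that also covers the two hands of bilateral participants. Name the visits entered, reconciling sections 8c and 9. Analyse all participants in the assigned arm. State the missing-data assumption, and add one sensitivity analysis for missing Visit Five scores with its own assumption stated; assigning the baseline value, for example, assumes no change. Participants with a baseline and at least one later score then contribute to the main model, and the sensitivity analysis covers those with a baseline only.

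**Section 8c.** State that participants who stop the assigned intervention, for whatever reason, stay in outcome collection. If they will not attend, send the self-reported scales by email at the Visit Five date and flag those scores by setting. This concerns data collection only and leaves the rules for stopping tape, splint or exercises as they are.

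**Cost.** Protocol wording, some added modelling work and a few emails; the protocol already emails reminders and results. The small downside is a mixed mode of collection. Classical repeated measures analysis of variance for grip and pinch also drops incomplete series, so the authors may wish to use the same type of model there.

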12. RISK AND INJURY

Participants may experience discomfort or skin irritation from wearing the tape, splint or completing the exercises. Participants may also experience fear and/or anxiety, and/or hyperventilation before during, or after application of Kinesio Tape, and/or splint, and/or exercises. Under these circumstances the Kinesio Tape will be removed from the participant's forearm wrist hand and provide first aid and seek medical care as needed. To minimize the potential of risks to participants the student researcher and student research assistants will ask if any known allergies to adhesives. Participants with a history or current allergy to adhesives will be excluded from the study. Risks may also include a participant may feel uncomfortable answering questions during interviewing. Loss of confidentiality may occur if two participants know each other. In order to protect confidentiality a number will be assigned to each participant. The master list and Informed Consent will be kept separate in the Principal Investigator's office.

13. BENEFIT (S)

The benefit of this study may help determine the validity of a non-surgical cost effective intervention that can be applied at the work site and allow for increased participation in occupations of daily living for carpal tunnel syndrome forearm wrist hand pain. Results of the study could provide insights to practitioners and researchers working with carpal tunnel syndrome forearm wrist hand pain and the influence of Kinesio Tape on occupational performance. Improving the understanding of terminology and inherent factors in current accepted protocols for carpal tunnel syndrome may be an additional benefit.

14. COMPENSATION

Participants will receive a \$5.00 gift card per visit for each of the five visits for the study.

15. CONFIDENTIALITY

Numbers will be used to identify participants and a coding sheet known only to the researcher will be kept in a locked office. All identifying information will be removed. Any published document resulting from this study will not disclose participant identity without written permission. All data will be secured in a locked cabinet in a locked office.

16. LITERATURE REVIEW

Musculoskeletal disorders are consistently considered sprains, strains, tears resulting from over exertion of the muscles during an activity and result in an injury to muscles, joints, ligaments, tendons, cartilage, or nerve (Lysaght, Donnelly, & Luong, 2010; United States Bureau of Labor, 2015). Upper extremity musculoskeletal injuries account for the second most common musculoskeletal disorder according to the United States Department of Labor (2015) with carpal tunnel syndrome the most frequently identified (41%) of all upper extremity repetitive movement disorders (Roll, 2016; United States Department of labor, 2015).

Carpal tunnel syndrome is a common neuropathy of the median nerve of the wrist with progressive intermittent signs and symptoms leading to impaired function and even muscle atrophy with nocturnal pain and paresthesia, decreased tactile sensation, and numbness in the first three fingers, as well as pain in the upper extremity, weakness of the hand and wrist (Ozgen et al., 2011). Carpal tunnel syndrome increases with age and three to one females to males experience symptoms with co-morbidities of diabetes and even pregnancy can be found to be contributing factors (Ozgen et al., 2011). Ali and colleagues (2013) concluded carpal tunnel syndrome may be caused from an increased pressure of the carpal tunnel, prolonged exposure to hand-arm vibrations, a combination of repetitive hand use and the use of hand force, and in recent years has expanded to include the use of computers and similar devices. It is believed that chronic repetitive use of the fingers and wrist may generate a shearing between the carpal tunnel, the median nerve, and the flexor tendons, which results in a restricted hyperplasia and fibrosis of the tenosynovitis of the flexor tendons and the median nerve in the tunnel (Ali et al., 2013).

Walker and colleagues (2000) identified individuals who work in highly repetitive environments have a significant chance of being diagnosed with carpal tunnel syndrome, for example individuals in manufacturing, service industry personnel such as hairdressers, massage therapists, gardeners, pet groomers, chefs, construction workers, and nurses are identified among this population. However, office workers are now included as Coggon and colleagues (2013) found workers who use the PC for 4-hours a day experience a high incidence of this disabling upper extremity musculoskeletal disorder of carpal tunnel syndrome. Goldfarb in (2016) furthered Coggon and colleagues (2013) study with findings that those who use computers and work 12 hour days over an 8-year span are primarily the at-risk population and could now include students. Common interventions for this disorder lack protocol, homogeneity, and consistency of results. Passive interventions are a patient's first choice, and at times a physician's but evidence based practice governmental regulation, as well as cost containment needs are pushing for increased and early worksite interventions, according to Lysaght and colleagues (2010). Accepted protocols include combining intervention modalities such as splinting and lumbrical exercises, with varied mediocre effectives and high issues surrounding patient compliance (Amini, 2011). In a systematic review Roll and Hardison (2016) found splinting type and position remain unstandardized.

One study using a combination of lumbrical stretching exercises and a general cock-up splint provided symptom relief up to 24 weeks, longer than any combination of conservative intervention (Baker et al., 2012; Manente et al., 2012). New evidence by Nadar et al. (2013)

found finger position can influence properties of the median nerve and Bulut et al. (2015) found the wrist positioned in neutral and metacarpophalanges supported provides the best outcomes. Kase et al. (1998) identified four principles of Kinesio Tape, that it supports muscles by improving muscle contraction, increases flow of body fluids, activates the endogenous analgesic system resulting in decreased pain, and corrects joint alignment based on application. Fourteen peer review studies between 2004 – 2014 provide evidence of KT for lower extremity pain and edema. Few and poor studies exist on upper extremity use of KT, such as with carpal tunnel syndrome and the Kase accepted method of Kinesio Tape application for carpal tunnel syndrome is on the flexor surface (palm of the hand and wrist) but has face validity only. However, if Kinesio Tape is to support or facilitate muscles based on application, as well as provide musculoskeletal re-positioning, and influence sub-acute pain, then using Kinesio Tape on the flexor surface would seemingly only increase compression on the median nerve by pulling the wrist and fingers into flexion/grip position. The application of Kinesio Tape on the extensor surface may reposition the wrist into neutral and open the carpal tunnel while supporting the metacarpophalanges. Thus, the purpose of this study is to determine if the dorsal application of Kinesio Tape applied to the wrist extensors for individuals with carpal tunnel syndrome, makes a difference in occupational performance of pain, strength, and function and to explore the perspectives of participants to understand if Kinesio Tape contributed to changes in occupational performance and compliance and if so, how.

References

American Occupational Therapy Association. (2014). Occupational therapy practice framework: Domain and process (3rd ed.). *American Journal of Occupational Therapy*, 68(Suppl. 1), S1–S48. <http://dx.doi.org/10.5014/ajot.2014.682006>

Amini, D. (2011). Occupational therapy interventions for work-related injuries and conditions of the forearm, wrist, and hand: A systematic review. *American Journal of Occupational Therapy*, 65, 29-36. <http://dx.doi.org/10.5014/ajot.2011.09186>

